10.1.2 Serious adverse events

An SAE is defined as any AE [appearance of (or worsening of any pre-existing)] undesirable sign(s), symptom(s), or medical conditions(s) which meets any one of the following criteria:

- fatal
- life-threatening

Life-threatening in the context of a SAE refers to a reaction in which the participant was at risk of death at the time of the reaction; it does not refer to a reaction that hypothetically might have caused death if it were more severe (please refer to the ICH-E2D Guidelines).

- results in persistent or significant disability/incapacity
- constitutes a congenital anomaly/birth defect
- requires inpatient hospitalization or prolongation of existing hospitalization, unless hospitalization is for:
 - routine treatment or monitoring of the studied indication, not associated with any deterioration in condition
 - elective or pre-planned treatment for a pre-existing condition that is unrelated to the indication under study and has not worsened since signing the informed consent
 - social reasons and respite care in the absence of any deterioration in the participant's general condition
 - treatment on an emergency outpatient basis for an event not fulfilling any of the definitions of a SAE given above and not resulting in hospital admission
- is medically significant; e.g. defined as an event that jeopardizes the participant or may require medical or surgical intervention to prevent one of the outcomes listed above

Medical and scientific judgment should be exercised in deciding whether other situations should be considered serious reactions, such as important medical events that might not be immediately life threatening or result in death or hospitalization but might jeopardize the participant or might require intervention to prevent one of the other outcomes listed above. Such events should be considered as "medically significant." Examples of such events are intensive treatment in an emergency room or at home for allergic bronchospasm, blood dyscrasias, or convulsions that do not result in hospitalization or development of dependency or abuse (please refer to the ICH-E2D Guidelines).

All new malignant neoplasms will be assessed as serious under "medically significant" if other seriousness criteria are not met and the malignant neoplasm is not a disease progression of the study indication.

Any suspected transmission via a medicinal product of an infectious agent is also considered a serious adverse reaction.

All reports of intentional misuse and abuse of the product are also considered SAE irrespective if a clinical event has occurred.

10.1.3 SAE reporting

To ensure participant safety, every SAE, regardless of causality, occurring after the participant has provided informed consent and until 30 days following the last administration of study treatment must be reported to Novartis safety immediately, without undue delay, but under no circumstances later than within 24 hours of obtaining knowledge of the events (Note: if more stringent, local regulations regarding reporting timelines prevail). Detailed instructions regarding the submission process and requirements are to be found in the investigator folder provided to each site.

For Screen Failures (e.g. a participant who is screened but is not treated or randomized), SAEs occurring after the participant has provided informed consent until the time the participant is deemed a Screen Failure must be reported to Novartis.

All follow-up information for the SAE including information on complications, progression of the initial SAE and recurrent episodes must be reported as follow-up to the original episode immediately, without undue delay, but under no circumstances later than within 24 hours of the investigator receiving the follow-up information (Note: if more stringent, local regulations regarding reporting timelines prevail). An SAE occurring at a different time interval or otherwise considered completely unrelated to a previously reported one must be reported separately as a new event.

If the SAE is not previously documented in the IB or Package Insert (new occurrence) and is thought to be related to the study treatment, a Chief Medical Office and Patient Safety (CMO & PS) Department associate may urgently require further information from the investigator for health authority reporting. Novartis may need to issue an Investigator Notification (IN) to inform all investigators involved in any study with the same study treatment that this SAE has been reported.

Suspected Unexpected Serious Adverse Reactions (SUSARs) will be collected and reported to the competent authorities and relevant ethics committees in accordance with EU Guidance 2011/C 172/01 or as per national regulatory requirements in participating countries.

Any SAEs experienced after the 30-day period following the last administration of study treatment should only be reported to Novartis Safety if the investigator suspects a causal relationship to study treatment.

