2.1 Primary estimand

The primary clinical question of interest is: does DFV890 prevent flares triggered by the cold challenge as indicated by proportional reduction in the fold change from pre-challenge to the highest post-challenge value of WCC between treatment and screening periods in participants with FCAS?

It has been shown ([Hoffman et al 2004](#)) that the fold change in WCC from pre-challenge to post-challenge can capture the treatment effect in the acute flare situation triggered by the cold challenge. Hence the choice of the primary estimand is considered as the ratio of fold change from pre-challenge to highest post-challenge WCC values between treatment and screening.

The primary estimand is described by the following attributes:

[figure not shown]
1. Population: participants with a genetic diagnosis of FCAS in association with a clinical history and investigations consistent with FCAS, who show evidence of inflammatory activity after the cold challenge performed during screening. Further details about the population are provided in [Section 5](#).
2. Endpoint: fold change from pre-challenge to the highest post-challenge value of WCC. This is measured as the ratio of highest post-challenge and the pre-challenge value of WCC. The highest post-challenge value is based only on post-challenge measurements within the cold challenge visit (up to and including 8 hours post-challenge; i.e. 9 hours post-dose).
3. Treatment of interest: DFV890
4. Summary measure: ratio of treatment fold change and screening fold challenge of WCC value.

3 Study design

This is an open-label, single-arm, multiple dose, phase II study to assess safety, tolerability and efficacy of DFV890 in participants with FCAS who show evidence of inflammatory activity after the cold challenge performed during screening. Approximately 6 participants with FCAS and confirmed NLRP3 gain-of-function mutations will be enrolled in the CDFV890A12201 study.

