4.6.2 Potential risks to study participants

The risk to participants with FCAS in this trial may be minimized by compliance with the eligibility criteria and study procedures, as well as close clinical monitoring, follow-up, minimal duration of the study treatment and pre-specified study stopping rules.

The cold challenge procedure was developed to study the acute inflammatory mechanisms after general cold exposure in FCAS patients and to investigate the effect of pretreatment with IL-1 blocking therapeutics to enable the clinical development of such therapeutics. Participants with a clinical history of transient self-limiting rash, fever and/or arthralgia that are pathognomonic of FCAS following cold exposure that resolve with warmth will undergo two controlled cold challenges while domiciled at the clinical site under medical supervision to trigger a transient and monitorable inflammatory response. Following the 45-minute cold challenge, participants will be returned to an ambient temperature of approximately 23°C for at least 24 hours at the clinical site, to ensure resolution of the inflammatory response.

The design of the cold challenge procedure is based on the clinical characteristics of the acute episodes in FCAS patients where a mean duration of generalized cold exposure of 52 minutes (range 5-180 minutes) was reported to trigger a self-limiting episode with onset of symptoms 150 minutes (range 10-480 minutes) after generalized cold exposure, with the absolute change in temperature (ambient to low) being an important factor in precipitating episodes (Hoffman et al 2001, Johnstone et al 2003). Importantly, environmental generalized cold exposure (e.g. cold damp weather) would similarly cause an inflammatory episode in many untreated FCAS patients experiencing baseline daily symptoms, often with diurnal pattern of episodes in the afternoon or evening that resolve by morning following rewarming in bed overnight. The cold challenge as described in the present protocol models the real life situation of exposure to mildly cold weather conditions and is expected to trigger typical signs and symptoms of an acute episode in FCAS patients including a low-grade fever, rash and arthralgia beginning approximately 1 hour after challenge, peaking at 4-8 hours and abating with warming by the next day with no reports of acute complications during the challenge or long-term sequelae in patients (Hoffman et al 2004, Ross et al 2008).

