5.1 Inclusion criteria

Participants eligible for inclusion in this study must meet **all** of the following criteria:

1. Written informed consent must be obtained before any study-specific assessment is performed.
2. Participants must be able to communicate well with the investigator and to understand and comply with the requirements of the study.
3. Male and female participants aged between 18 - 80 years (for France 18 - 60 years) inclusive at the time of screening will be included.
4. Participants must have a body mass index (BMI) within the range of 18 - 35 kg/m² (BMI = Body weight (kg) / [Height (m)]²) at Screening, Screening Cold Challenge Admission visit and Day 1 pre-dose.
5. Participant with a genetic diagnosis of FCAS (this analysis may be performed as part of screening if not readily available).
6. Clinical history and investigations consistent with FCAS, in the absence of a history or diagnosis of amyloidosis and/or organ damage (e.g. deafness, periorbital edema, lymphadenopathy, and serositis).
7. Evidence of inflammatory disease activity during the screening period before the admission to the screening cold challenge, captured by the Physician global assessment of autoinflammatory disease activity > minimal, recorded at Screening Cold Challenge Admission visit.
8. Participants who have evidence of inflammatory activity after the screening cold challenge, as assessed by a relative increase in WCC of at least 40% compared to pre-challenge.

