8.1.2 Information to be collected on screening failures

Participants who sign an informed consent form and subsequently found to be ineligible will be considered a screen failure. This applies also to participants who are considered screen failures after the screening cold challenge. The reason for screen failure should be entered on the

applicable eCRF. The demographic information, informed consent, and Inclusion/Exclusion pages must also be completed for screen failure participants. Additional data may be entered to support the eligibility decision, such as – but not limited to – medical history, relevant prior and concomitant medications, hematology, clinical chemistry. SAEs will also be collected for screen failed participants (see SAE section ([Section 10.1.3](#)) for reporting details).

Participants who sign an informed consent and are considered eligible but fail to be started on treatment for any reason will be considered an early terminator. The reason for early termination should be captured on the appropriate disposition eCRF.

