9.1.4 Study stopping rules

Overall study stopping rules

The study will be stopped, and no further dosing and/or new recruitment will occur, pending full safety review by the sponsor and the investigator, if any of the following criteria are met:

- Any death or life-threatening event (corresponding to CTCAE grade 4 or higher) unless clearly unrelated to DFV890 and/or the cold challenge
- Any SAE (other than death or life-threatening event, corresponding to CTCAE grade 3 or higher) unless clearly unrelated to DFV890 and/or the cold challenge
- Two (2) or more participants are discontinued due to a renal event as defined in [Section 16.2](#)
- Two (2) participants experience an AE of similar type which is assessed as severe in intensity (corresponding to CTCAE grade 3 or higher) unless clearly unrelated to DFV890
- Number and/or severity of AEs, abnormal safety monitoring tests, or abnormal laboratory findings justify putting the study on hold

The safety review will be conducted jointly between medically qualified representatives of the sponsor and the investigators. The study may resume following the safety review, if the investigator and sponsor agree it is safe to proceed and necessary approvals have been obtained from authorities.

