9.2 Study completion and post-study treatment

Study completion is defined as when the last participant finishes their Study completion visit and any repeat assessments associated with this visit have been documented and followed-up appropriately by the Investigator or, in the event of an early study termination decision, the date of that decision. Each participant will be required to complete the study in its entirety and thereafter no further study treatment will be made available to them.

All treated participants should have a safety follow-up call conducted 30 days after last administration of study treatment. The information collected is kept as source documentation. All SAEs reported during this time period must be reported as described in [Section 10.1.3](#). Documentation of attempts to contact the participant should be recorded in the source documentation.

Continuing care should be provided by the investigator and/or referring physician. No further study treatment will be provided.

10 Safety monitoring and reporting

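### For a participant who fails screening after the cold challenge, mandatory SAE reporting ends when failure is declared, so a later challenge-related SAE need not reach the Section 9.1.4 stopping rule

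*Protocol*

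**What the plan says.** **Screen failures.** Protocol Section 10.1.3 sets a separate SAE window for them: "SAEs occurring after the participant has provided informed consent until the time the participant is deemed a Screen Failure must be reported to Novartis". Section 8.1.2 defines the status and adds: "This applies also to participants who are considered screen failures after the screening cold challenge". It also states that "SAEs will also be collected for screen failed participants", but refers to Section 10.1.3 for the details and gives no longer window.

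**Stopping rule.** One criterion in Section 9.1.4 is: "Any SAE (other than death or life-threatening event, corresponding to CTCAE grade 3 or higher) unless clearly unrelated to DFV890 and/or the cold challenge". Nothing there confines it to participants who received DFV890. Meeting a criterion halts dosing and/or recruitment pending a safety review. Section 9.1.1 and Appendix 3 also make it a reason to stop a cold challenge.

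**The deciding test.** Inclusion criterion 8 requires inflammatory activity after the screening challenge, "as assessed by a relative increase in WCC of at least 40% compared to pre-challenge". It gives no time point. Footnote 19 of Table 8-1 says all other criteria are confirmed before admission to the challenge.

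**Treated participants.** SAEs are reportable until 30 days after the last dose. Section 9.2 says: "All treated participants should have a safety follow-up call conducted 30 days after last administration of study treatment". Footnote 15 of Table 8-1 agrees, but the table itself puts the contact at Day 34 ±3.

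**The concern.** The cold challenge is a study procedure with its own stopping criteria. It is given to everyone who reaches that stage of screening, including people who will never be dosed. The protocol expects the reaction to run over many hours, "beginning approximately 1 hour after challenge, peaking at 4-8 hours and abating with warming by the next day". Failing criterion 8 means only that the white cell count (WCC) did not rise enough. It does not rule out a serious cold-related event.

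If failure is declared while the reaction is still running, or before a delayed event appears, a site that follows Section 10.1.3 exactly has no duty to send a new SAE to the sponsor. For screen failures, Section 8.1.2 requires only the failure reason, demographics, consent and eligibility pages, and SAEs, so SAE reporting is the one mandatory route for such an event. In a study of about 6 participants, where a single qualifying SAE triggers a pause, one unreported event could let further challenges continue when the protocol intends a review.

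**Working it through.** **1. Scope of the duty against scope of the rule**

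| | Who | Until when |
|---|---|---|
| 10.1.3, general duty | any consented participant | 30 days after last dose (undefined if never dosed) |
| 10.1.3, screen failures | includes post-challenge failures, by 8.1.2 | the moment failure is declared |
| 10.1.3, late SAEs | after the 30-day period | only if suspected to be caused by study treatment; the challenge is not named |
| 9.1.4, stopping rule | not limited to dosed participants | no end stated; covers DFV890 and/or the challenge |

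A new challenge-related SAE that starts after failure is declared is in scope of the last row and outside the duty in the first three.

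**2. How much scheduled observation could be affected**

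Inputs from Table 8-1 and its footnotes 7 and 26: the screening clock starts at the meal, the challenge starts at 1 h and lasts 45 minutes (ending at 1.75 h), and assessments include 9 h and 24 h. Section 2.1 closes the primary WCC peak window at "up to and including 8 hours post-challenge; i.e. 9 hours post-dose".

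- 9 h point: 9 − 1 = 8 h after the start of the challenge; 9 − 1.75 = 7.25 h after its end. Both are within the stated 4-8 h peak.
- 24 h point: 24 − 1 = 23 h after the start; 24 − 1.75 = 22.25 h after the end.
- Interval between them: 24 − 9 = 15 h.

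The time of declaration is not given, so the result is a range:

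- Declared on a same-day 9 h WCC (assumption): up to 15 h of scheduled observation outside the duty, less laboratory turnaround.
- Declared at or after discharge: 0 h of scheduled observation outside it, but anything that begins later is still uncovered.

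A same-day result is plausible, because footnote 8 asks for WCC to be drawn with hematology where possible and Section 8.4.1 has safety samples analysed locally. No section states it.

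**3. Safety contact for treated participants**

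Reproducing the plan's figure: Day 4 + 30 = Day 34, as in Table 8-1. The ±3 window is Day 31 to Day 37.

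| Last dose | 30 days after | Contact window, days after last dose | Earliest contact falls short by |
|---|---|---|---|
| Day 4 | Day 34 | 31 − 4 = 27 to 37 − 4 = 33 | 3 days |
| Day 5 (allowed by 6.5) | Day 35 | 31 − 5 = 26 to 37 − 5 = 32 | 4 days |

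With a Day 5 last dose, nominal Day 34 is itself 34 − 5 = 29 days. A window of −0/+3 from the actual last dose + 30 gives Day 34-37 or Day 35-38, with no shortfall.

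**The case against.** **Reporting is a minimum, and the rule triggers on events.** Section 10.1.3 forbids nothing, and an investigator may report voluntarily. Section 9.1.4 does not refer to SAE forms. It also lists death or life-threatening events and a general criterion on the number or severity of AEs, and its review is joint between sponsor and investigators. This stands. A reader might infer that a late SAE cannot reach the stopping rule; the text supports only that it need not.

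**Observation continues.** Participants stay domiciled until the last scheduled assessment whatever their WCC. An SAE that starts before declaration is reportable, and its progression must be sent as follow-up. Section 10.1.1 also requires AEs to be followed to resolution. This stands too: the gap is in the reporting duty for a new event, not in bedside care.

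**The timing is not documented.** A reader might infer that criterion 8 is decided 8 h after the challenge. That limit belongs to the primary endpoint. The eligibility criterion has none, and the WCC sampling row for the challenge visits cannot be read in the public text. The eligibility row, as it can be read, has entries only at Screening, Admission and Day 1. The 15 h is therefore an upper figure under an assumption.

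**Comparison with dosed participants.** It would be misleading to set this cut-off against the 30-day window, which follows drug exposure. Undosed people need not share it.

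**Low expected frequency.** Section 4.6.2 cites no acute complications during the challenge and no long-term sequelae. That lowers the probability but does not remove the mismatch, since the sponsor wrote challenge-related SAEs into the stopping rule.

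**Possible backstop.** The glossary definition of study treatment includes interventions, which might bring the challenge under the late-SAE clause. Section 6.1.2 says the trial includes no treatment beyond the investigational drug, and the screen-failure window is separate and shorter in any case. The backstop is not secure.

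**Safety contact.** A ±3-day tolerance on a call is ordinary, and the Day 5 case is exceptional. A reader might infer that SAE reporting for treated participants closes early. It does not: the 30-day duty holds whenever the call is made.

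**Conclusion.** The point holds as a gap in wording. Read together, Sections 10.1.3 and 8.1.2 end the mandatory duty for a challenged participant when failure is declared, while Section 9.1.4 relies on challenge-related SAEs from anyone challenged. A new SAE after declaration may go unreported without any breach of protocol.

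The size is 0 to about 15 h of scheduled observation, depending on an undocumented time of declaration, plus any event beginning after discharge. The documents give neither the number of challenged screen failures expected nor a rate of serious reactions, so no probability can be attached. The change is still worth making, because one event would trigger the pause and the correction costs very little.

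The safety-contact mismatch is a minor scheduling inconsistency. The last planned contact can fall 3 days before the 30-day period ends (4 days with a Day 5 last dose).

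**What to change.** **Sections 10.1.3 and 8.1.2.** For anyone who started the screening cold challenge, keep SAE reporting open regardless of screen-failure status, at least through discharge and preferably through the one-week recovery interval the protocol already uses (Section 3; footnote 20 of Table 8-1). Require reporting of any later SAE suspected to be related to the challenge. The one-week end point is a choice: the protocol uses that interval for participants going on to Day 1, not as a safety window for screen failures. Wording by exposure to the challenge also covers the early terminators of Section 8.1.2, who are found eligible but never dosed and for whom Section 10.1.3 gives no clear end date.

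If discharge becomes the minimum, reconcile the stated stay: Section 4.6.2 gives about 22 h after the end of the challenge and also at least 24 h on site, and Appendix 3 gives at least 24 h.

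**Table 8-1.** Anchor the post-study safety contact to the actual last dose + 30 days with a −0/+3 window, in line with Section 9.2 and footnote 15. The completion visit already uses a −0 lower limit.

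**Cost.** Amendment wording, a slightly longer reporting duty and at most a brief status check for a few screen failures, and a little less flexibility in scheduling one call.
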